### **Time to response (TTR)**

TTR is defined as the time from the first dose of study treatment to the first occurrence of CR, CRi, PR, nPR, VGPR, PR-L, or MR. Only patient with response of CR, Cri, PR, nPR, VGPR, PR-L, or MR will be included in the analysis for TTR.

$TTR = ([\text{date of first response}] - [\text{date of first dose of study medication}] + 1) / 30.4375$ . Median TTR along with the two-sided 95% CI will be estimated using Kaplan-Meier method. The 95% CI for the median will be calculated using a log-log transformation based on Brookmeyer and Crowley (Brookmeyer, R., & Crowley, J. 1982) method. Kaplan-Meier curve will be plotted by dose level in Stage 1 and by the malignancy type in Stage 2.

### **Tumor Burden**

Tumor burden is defined as the sum of the product of diameters of all target measurable lesions at each tumor assessment visit.

The best percent change from baseline in tumor burden is calculated as:

$(\text{The minimum tumor burden among post-baseline assessments} - \text{Baseline tumor burden value}) / \text{Baseline tumor burden value} \times 100$

Tumor burden will be missing for that assessment visit if there is a missing value of the product of diameters. Thereof a patient will be considered not evaluable for the measure of the best percent change from baseline in tumor burden.

A waterfall plot will be presented for all patients. Different color will be presented to differentiate various dose levels (for Stage 1) and the different type of malignancy in Stage 2.

A listing with the tumor assessments at baseline and each tumor assessment visit will be presented.

The PET-CT Examination will also be listed.

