5.6.12 Tumor and Response Evaluation

All evaluable lesions should be assessed and documented at screening and re-assessed at each subsequent tumor evaluation, using blood test, physical examination, and contrast-enhanced CT scans (neck, chest, abdomen, and pelvis) for indolent NHL and/or positron emission tomography (PET)-CT for HL and aggressive NHL. Enhanced magnetic resonance imaging (MRI) may be used instead of enhanced CT scans in patients for whom CT scans are contraindicated.

Tumor assessment will be conducted every 8 weeks (± 7 days) for the first 24 weeks and every 12 weeks (± 7 days) thereafter until the patient has the first progression, starts new anticancer therapy, or dies. Patients who discontinue study drug due to reasons other than disease progression will remain on the study and will be followed quarterly for tumor assessment until the patient has their first progression, starts new anticancer therapy, or dies or until 12 months after their initial dose of the study drug. Tumor assessment will also be conducted at study completion or early termination (for reasons other than disease progression).

The same imaging procedure and laboratory tests used to define evaluable lesions at baseline should be used throughout the study for each patient.

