#### Best overall response (BOR)

The best overall response (BOR) for an individual patient is the best response recorded from the start of treatment until progression or the date of any further anticancer therapy, whichever comes first.

Best overall response is determined from the sequence of responses assessed as below:

- For CLL guideline: Complete Response (CR), CR with incomplete bone marrow recovery (CRi), Partial Response (PR), Nodular Partial Response (nPR), Partial Response with Lymphocytosis (PR-L), Stable Disease (SD), Progressive Disease (PD), Not all evaluated (NE).
- For WM guideline: Complete Response (CR), Very Good Partial Response (VGPR), Partial Response (PR), Minor Response (MR), Stable Disease (SD), Progressive Disease (PD), Not Evaluated (NE).
- For Other Lymphomas guideline: Complete Response (CR), Partial Response (PR), Stable Disease (SD), Progressive Disease (PD), Not Evaluated (NE).

For patients with multiple assessment for same visit, the earliest date will be selected for PD, while the latest date will be selected for other response.

Patients with BOR "NE" will be summarized by reason for having NE status. The following reasons will be used:

- No valid post-baseline assessment
- All post-baseline assessments have overall response NE

Patients with a BOR of "Unknown" or "NE" will be considered non-responders in estimating response rates.

HMPL-523

The number and percentage of patients with BOR of CR, CRi, VGPR, PR, nPR, MR, PR-L, SD, PD, and NE will be summarized by dose level and overall in Stage 1, by the malignancy type and overall in Stage 2.

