### **Progression free survival (PFS)**

PFS is defined as the time (in months) from the date of first study medication to the earliest date of disease progression or death due to any reason whichever occurs first.

HMPL-523

PFS (months) = ([date of progression or death or censoring] - [date of first dose of study medication] + 1)/30.4375.

A patient is deemed to be censored according to the rules specified in **Error! Reference source not found.** below.

Error! Reference source not found.: **Progression-Free Survival Censoring Rules**

#	Situation	Date of Progression or Censoring	Outcome	Event/Censor reason
1	Death (without previously documented progressive disease [PD]) within two evaluable tumor assessments [a] from last evaluable tumor assessment or first dose (if no post-baseline tumor assessment)	Date of death	Event	Death
2	Death (without previously documented PD) after two or more consecutive missed/non-evaluable tumor assessments [a] from last evaluable tumor assessment or first dose (if no post-baseline tumor assessment)	Date of last evaluable tumor assessment or date of first dose (if no post-baseline tumor assessment)	Censored	Death after two or more consecutive missed or NE tumor assessments
3	Progression within two evaluable tumor assessments [a] from last evaluable tumor assessment or first dose (if no post-baseline tumor assessment before PD)	Date of progression	Event	Disease Progression
4	Progression after two or more consecutive missed/non-evaluable tumor assessments [a] from last evaluable tumor assessment or first dose (if no post-baseline tumor assessment before PD)	Date of last evaluable tumor assessment or date of first dose (if no post-baseline tumor assessment before PD)	Censored	Progression after two or more consecutive missed or NE tumor assessments
5	Progression after new anti-cancer treatment	Date of last evaluable tumor assessment before new anti-cancer treatment or date of first dose (if no post-baseline tumor assessment before new anti-cancer)	Censored	Progression after new anti-cancer therapy
6	No baseline tumor evaluable assessment and alive	Date of first dose	Censored	No baseline assessment
7	No post-baseline tumor evaluable assessment and alive	Date of first dose	Censored	No post-baseline assessment

HMPL-523

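### The waterfall measure has no stop at progression or new therapy, and its missing-data sentence, read literally, drops a patient for one incomplete visit

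*SAP*

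**What the plan says.** SAP 16.1.1 (Tumor Burden) defines burden at a visit as the sum, over the target lesions, of the product of diameters. The best percent change is then taken from "The minimum tumor burden among post-baseline assessments", relative to baseline.

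Two sentences deal with missing values. The first works at visit level: "Tumor burden will be missing for that assessment visit if there is a missing value of the product of diameters". The second moves to the patient: "Thereof a patient will be considered not evaluable for the measure of the best percent change from baseline in tumor burden". The display is then described: "A waterfall plot will be presented for all patients". No analysis set is named for it.

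The neighbouring endpoints in 16.1.1 have an explicit window. BOR is the "best response recorded from the start of treatment until progression or the date of any further anticancer therapy, whichever comes first". PFS is censored at the last evaluable scan no later than the start of new therapy, and a scan on the day new therapy starts is treated as preceding it.

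Protocol 5.6.12 continues the 12-weekly scans "thereafter until the patient has the first progression, starts new anticancer therapy, or dies". It also requires a tumor assessment at completion or early termination when the reason is not progression. The schedule in Protocol Appendix 1 places that visit 30 ± 7 days after treatment ends.

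**The concern.** The first problem is the window. A scan that BOR and PFS exclude because it follows progression or new therapy is still eligible for the tumor-burden minimum. If the next treatment shrinks the target lesions, the bar for that patient shows that shrinkage as though it belonged to HMPL-523.

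The second problem is the patient-level sentence. It follows directly from the visit-level rule and carries no condition such as an incomplete baseline or no complete post-baseline visit. A programmer who follows it literally would remove a patient who has other complete visits.

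At stake is one display of preliminary efficacy, which is a primary objective in the expansion stage. Two programmers working from the same text could produce different plots.

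**Working it through.** The plan states no figure for this measure, so there is nothing to reproduce. The check has two parts.

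**Part 1: the window**

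| Measure (SAP 16.1.1) | Stops at progression? | Stops at new anticancer therapy? |
|---|---|---|
| BOR | Yes | Yes |
| PFS | Progression is the event | Yes, last evaluable scan no later than the start |
| Tumor-burden minimum | Not stated | Not stated |

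Which scans could fall in the gap?

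- Scheduled scans end at first progression or new therapy (Protocol 5.6.12), so they contribute little.
- The completion or early-termination scan is not required after progression. It can follow new therapy if a patient stops for another reason and starts the next treatment before that visit.
- Unscheduled assessments are allowed when clinically indicated (Protocol 5.6.1), and SAP 7.4 lets unscheduled measurements contribute to best and worst values.

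One such scan can dominate a minimum. Take a hypothetical patient with baseline 2000 mm², then 1800 and 1700 on study drug, then 800 at a completion visit after new therapy has started:

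- SAP formula: (800 − 2000)/2000 = −60%.
- Stopping at new therapy: (1700 − 2000)/2000 = −15%.

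**Part 2: the missing-visit rule**

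Inputs:

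- Patients: Protocol 4.5, Table 2, counting expansion cohorts for which inclusion criterion 6 requires measurable disease: HL 25 + FL 2 + MCL 2 + MZL 1 + PTCL 9 + CBCL 0 = 39 of the 48 enrolled.
- Post-baseline scans per patient: k = 3 (weeks 8, 16 and 24).
- Probability that a visit is incomplete: q. The documents give no value, so q = 2%, 5% and 10% are assumed, independent across visits.

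Formulas, with baseline taken as complete:

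- Literal reading, where any incomplete visit removes the patient: 1 − (1 − q)^k.
- Visit-level reading, where the patient is lost only if every visit is incomplete: q^k.

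| q | Literal: share lost | Literal: of 39 | Visit-level: share lost |
|---|---|---|---|
| 2% | 1 − 0.98³ = 5.9% | 2.3 | 0.0008% |
| 5% | 1 − 0.95³ = 14.3% | 5.6 | 0.0125% |
| 10% | 1 − 0.90³ = 27.1% | 10.6 | 0.1% |

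The literal loss grows with follow-up. With k = 5 (to week 48) it is 9.6%, 22.6% and 41.0%.

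**The case against.** **Scans after these events are rare by design.** Treatment stops at progression (Protocol 5.7.3), scheduled scans stop at progression or new therapy, and the completion scan is not required after progression. This stands, and it keeps the number of affected patients small. It governs what is collected, however, not what is analysed. BOR and PFS carry explicit cut-offs under the same schedule.

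**The PFS table does not prove that such scans exist.** A reader might infer from the row headed "Progression after new anti-cancer treatment" that the SAP expects scans after new therapy. The documents do not support that. A censoring table lists contingencies, and Protocol 6.4.8 allows progression to be determined from symptoms without supporting measurements, so the row need not involve a scan.

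**The patient-level sentence is ambiguous.** It may have been meant for an incomplete baseline, or for a patient with no complete post-baseline visit, where non-evaluability is right. The visit-level rule just before it would serve little purpose for this measure if one incomplete visit removed the patient. SAP 7.9 sets a general convention of using whatever data are available. This stands as evidence of likely intent. It also shows that the literal reading conflicts with the rest of the plan, and the words contain no limit that settles the matter.

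**Disagreement with BOR is not in itself a defect.** The Lugano criteria allow complete metabolic response with a residual mass, and a new lesion is progression whatever the target lesions do. This stands: the plot and BOR can differ under perfect rules.

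**The consequence is minor.** Tumor burden is not among the efficacy outcome measures in Protocol 4.8.4, and the SAP lists every tumor assessment, so an affected bar can be traced. This also stands.

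**Conclusion.** The point holds as a drafting defect in a descriptive display. The minimum has no stop at progression or new therapy, and the rule as written would count any scan after those events. Few are expected. The patient-level sentence, read literally, excludes a patient for one incomplete visit.

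Under the assumed 2% to 10% per visit, independence and three scans, that reading loses about 6% to 27% of 39 patients (about 2 to 11). Setting only the visit to missing loses 0.1% or less. The base of 39 leaves out Stage 1, whose patients are also plotted, and would be slightly larger if the CLL cohorts include SLL patients.

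Three stronger readings are not supported:

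- That the plot will in fact credit other drugs. The documents show only that the rule permits it.
- That about 5 of 48 bars would be lost needlessly (10% of 48 = 4.8). That uses a single assumed rate, and the 48 include CLL and WM/LPL patients, for whom measurable disease is not required. It also treats every affected visit as dispensable, when some could be the baseline or the only post-baseline scan.
- That incomplete visits are informative. Nothing in the documents bears on this.

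ORR, DoR and PFS have their own rules and are unaffected.

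**What to change.** Amend SAP 16.1.1 (Tumor Burden) as follows:

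- Take the minimum over complete post-baseline assessments up to and including first PD and no later than the start of new anticancer therapy, with the same-day convention already used for PFS.
- Set only the incomplete visit to missing.
- Call a patient not evaluable only if baseline is missing or incomplete, or if no post-baseline visit in that window is complete.
- Footnote the waterfall plot with the number of patients excluded and the reasons.

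This costs a few sentences and a small programming change, with no new data. SAP section 2 allows revision before final database lock.

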## **17. SAFETY OUTCOMES**

All outputs for safety outcomes will be based on the FAS with the exception of DLT which will be based on DLT evaluable analysis set.

HMPL-523

---

## 17.1. DLTs

A DLT is a toxicity or AE occurring in the first cycle (28 days), which is attributable to HMPL-523 and meets the criteria defined in the protocol. All DLTs are recorded in the eCRF page of “DLT Assessment”. The toxicities or AEs will be graded according to National Cancer Institute (NCI) - Common Terminology Criteria for Adverse Events (CTCAE) Version 5.0.

A summary of DTLs in stage 1 will be presented based on DLT Evaluable Set. For each dose level of HMPL-523 and overall, the following will be provided:

- Number of patients enrolled
- Number of patients in DLT Evaluable Set
- Number of patients with a DLT
- Number of DLTs by DLT category SOC and PT

A listing will present all DLTs by subject and dose level. The by-subject DLT data listings will include at a minimum verbatim term, PT, SOC, NCI-CTCAE grade, and relationship to HMPL-523.

## 17.2. ADVERSE EVENTS

Treatment-emergent adverse events (TEAEs) are defined as AEs with an onset date on or after the first dose of study medication and no later than 30 days after the date of last study treatment administration or start of a new treatment of anti-neoplasm therapy, whichever is earlier. An exception is that study medication related SAE collected later than 30 days after the last treatment date or start of a new treatment of anti-neoplasm therapy will be treated as TEAEs.

Refer to [Section 7.9](#) for handling of partial dates for AEs. In the case where it is not possible to classify an AE as treatment-emergent or not, the AE will be classified as treatment-emergent.

An overall summary of AEs will include the number of patients with:

- Any AE
- Any TEAE
- Any TEAE of CTCAE Grade 3 or higher
- Any TEAE of CTCAE Grade 3
- Any TEAE of CTCAE Grade 4
- Any TEAE of CTCAE Grade 5
- Any Treatment Related TEAE
- Any Treatment Related TEAE of CTCAE Grade 3 or higher
- Any Treatment Related TEAE of CTCAE Grade 3

HMPL-523

- 
- Any Treatment Related TEAE of CTCAE Grade 4
  - Any Treatment Related TEAE of CTCAE Grade 5
  - Any Serious TEAE
  - Any Serious TEAE of CTCAE Grade 3 or higher
  - Any Serious TEAE of CTCAE Grade 3
  - Any Serious TEAE of CTCAE Grade 4
  - Any Serious TEAE of CTCAE Grade 5
  - Any Treatment Related Serious TEAE
  - Any Treatment Related Serious TEAE of CTCAE Grade 3 or higher
  - Any Treatment Related Serious TEAE of CTCAE Grade 3
  - Any Treatment Related Serious TEAE of CTCAE Grade 4
  - Any Treatment Related Serious TEAE of CTCAE Grade 5
  - Any TEAE Leading to Dose Reduction
  - Any TEAE Leading to Drug Interruption
  - Any TEAE Leading to Drug Discontinuation
  - Any TEAE Leading to Death
  - Any TEAE of Special Interest (AESI)

Listings will include the following:

- All AEs
- All SAEs
- AEs leading to Drug Discontinuation
- AEs Leading to Death
- All AESIs

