7.3.3.2 Adverse Events

All AEs will be coded using the Medical Dictionary for Regulatory Activities (MedDRA), and the corresponding intensity will be graded according to NCI CTCAE v5.0.

Summaries will be presented for TEAEs. An AE is considered a TEAE if the onset date is on or after the start of study treatment or if the onset date is missing, or if the AE has an onset date before the start of study treatment but worsened in severity after the study treatment until 37 days after the last dose of study treatment. All TEAEs will be listed and the frequency of patients reporting TEAEs will be summarized by MedDRA System Organ Class and Preferred Term and NCI CTCAE grade.

The same analysis will be performed for SAEs; causality-related TEAEs assessed by the investigators; AEs leading to dose interruption, reduction, or treatment discontinuation; and protocol-defined AEs of special interest.

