### **7.3. ON TREATMENT PERIOD AND WORST POST-BASELINE**

For the analysis purpose, on treatment period is defined as the period from the day of first dose of treatment to 37 days after the last dose of treatment or the initiation of new antineoplastic therapy, whichever comes earlier.

The severity of adverse events and laboratory results depends on CTCAE grade. The worst post baseline value is defined as the highest CTCAE grade during on treatment period.

The worst post-baseline abnormality is defined in the order of Abnormal, Clinically Significant>Abnormal, Not Clinically Significant>Normal during the on-treatment period.

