**Error! Reference source not found.: Visit Window**

	Cycle 1			Cycle 2		Cycle 3 and onwards	Last Cycle	Follow-up		
	D1	D8 (±1)	D15 (±1)	D22 (±1)	D1 (±3)	D15 (±3)	D1 (±3)	CXD1	Study Completion or Early Termination (30±7 Days After the End of Treatment)	Follow-up on Day 1 (±7) Quarterly After the End of Treatment
Scheduled Day [a]	1	8	15	22	1	15	1	1		
ECOG performance status	Day1		2 to EOC-3		Day -3 to 8	9 to EOC-3	Day -3 to EOC-3	Day-3 to EOC	Last dose date of last cycle +1 to last dose date of last cycle +37	
Vital signs	Day1	2 to 11	12 to 18	19 to EOC-3	Day -3 to 8	9 to EOC-3	Day -3 to EOC-3	Day-3 to EOC		

HUTCHMED Ltd.

CONFIDENTIAL

HMPL-523

									Follow-up	
	Cycle 1				Cycle 2		Cycle 3 and onwards	Last Cycle		
	D1	D8 (±1)	D15 (±1)	D22 (±1)	D1 (±3)	D15 (±3)	D1 (±3)	CXD1	Study Completion or Early Termination (30±7 Days After the End of Treatment)	Follow-up on Day 1 (±7) Quarterly After the End of Treatment
Hematology		1 to 11	12 to 18	19 to EOC-3	Day -3 to 8	9 to EOC-3	Day -3 to EOC-3	Day-3 to EOC		
Urinalysis/ dipstick			1 to EOC-3		Day -3 to 8	9 to EOC-3	Day -3 to EOC-3	Day-3 to EOC		
Chemistry panel		1 to 11	12 to 18	19 to EOC-3	Day -3 to 8	9 to EOC-3	Day -3 to EOC-3	Day-3 to EOC		
Beta 2-microglobulin					Cycle 1 Day 1 to EOC-3		Day -3 to EOC-3	Day-3 to EOC		
Fasting lipid profile					Cycle 1 Day 1 to EOC-3		Day -3 to EOC-3	Day-3 to EOC		
Serum amylase and lipase		1 to 11	12 to 18	19 to EOC-3	Day -3 to 8	9 to EOC-3	Day -3 to EOC-3	Day-3 to EOC		
Coagulation assay (INR, aPTT, PT)					Cycle 1 Day 1 to EOC-3		Day -3 to EOC-3	Day-3 to EOC		
Leukocyte immunophenotyping			1 to EOC-3		Day -3 to EOC-3		Day -3 to EOC-3	Day-3 to EOC		
Echocardiogram/MUGA										

HUTCHMED Ltd.

CONFIDENTIAL

HMPL-523

								Last Cycle	Follow-up	
	Cycle 1				Cycle 2		Cycle 3 and onwards			
	D1	D8 (±1)	D15 (±1)	D22 (±1)	D1 (±3)	D15 (±3)	D1 (±3)		CXD1	Study Completion or Early Termination (30±7 Days After the End of Treatment)
12-Lead ECG	Day 1-2		3 to EOC -3		Day -3 to EOC -3		Day -3 to EOC -3	Day -3 to EOC		
Quantitative serum immunoglobulin levels (for WM/LPL)					Cycle 1 Day 1 to EOC -3		Day -3 to EOC -3	Day -3 to EOC		X
CT/PET-CT							Cycle 1 Day 1 to EOC -3	Day -3 to EOC		X

[a] The scheduled day is relative to Day 1 of each cycle.

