### Adverse Events

If the adverse event onset date is missing or partial, the date will be compared as far as possible with the date of first dose of study medication. Adverse events will be assumed to be treatment-emergent, unless there is clear evidence (through comparison of partial dates) to suggest that the adverse event started prior to the first dose of study medication or more than 30 days after last dose of study medication or new antineoplastic therapy.

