## 14. CONCOMITANT MEDICATIONS AND PROCEDURES

### 14.1. PRIOR AND CONCOMITANT MEDICATIONS

Medications will be presented for the FAS and will be coded using WHO-DDE version SEPT 2024.

Refer to [Section 7.9](#) for handling of missing or partial dates. In the case where it is not possible to define a medication as prior or concomitant based on dates, the medication will be classified as concomitant.

‘Prior’ medications are medications which started and stopped prior to the day of the first administration.

‘Concomitant’ medications are those which:

- Started prior to the first administration date of study medication and ended on or after the first administration date on treatment.
- Started on or after the first administration date of study medication but no later than 37 days following last administration date on treatment or start of a new treatment of anti-neoplasm therapy, whichever is earlier.

Prior and concomitant medications will be presented by ATC level 2 text and PT. ATC class and PT will be sorted in descending frequency of the total number of patients with at least one condition in the corresponding category, ATCs/PTs will be presented alphabetically for ATCs/PTs of the same total frequency.

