### 14.2. CONCOMITANT PROCEDURES

Concomitant procedures are defined as procedures that occurred at any time on or after the day of the first administration and no later than 37 days following the last administration date on treatment of study medication or start of a new treatment of anti-neoplasm therapy, whichever is earlier. Procedures will be presented for the FAS and will be coded using MedDRA Version 27.1 or higher. Concomitant procedures will be summarized and listed by SOC and PT. Number of patients and percentage in the analysis set will be presented in frequency tables, ordered by

HMPL-523

primary SOC and PT in descending order of the frequency in total group. For SOC's or PT's with the same frequency, categories will be sorted alphabetically.

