### 17.4. LABORATORY EVALUATIONS

The following laboratory evaluations will be summarized in tables:

- Chemistry
- Coagulation
- Fasting lipid profile
- Hematology
- Leukocyte immunophenotyping
- Serum immunoglobulin
- Serum amylase and lipase
- Serum  $\beta$ -2 microglobulin
- Urinalysis

The following laboratory evaluations will be listed in listings:

- Chemistry
- Coagulation
- Fasting lipid profile

HMPL-523

- 
- Hematology
  - Leukocyte immunophenotyping
  - Serum immunoglobulin
  - Serum amylase and lipase
  - Serum  $\beta$ -2 microglobulin
  - Urinalysis
  - Pregnancy test
  - Viral serology

Quantitative laboratory measurements reported as “< X”, i.e. below the lower limit of quantification (LLQ), or “> X”, i.e. above the upper limit of quantification (ULQ), will be converted to X for the purpose of quantitative summaries, but will be presented as recorded, i.e. as “< X” or “> X” in the listings.

Descriptive statistics for all quantitative laboratory evaluations and change from the baseline will be presented in SI units for each visit.

For laboratory parameters graded by NCI CTCAE, version 5.0 (see [Appendix 2](#)), changes in CTC grade laboratory data will be summarized as shift table from baseline to worst post-baseline grade. Baseline CTCAE grade is derived from the last laboratory assessment prior to the first administration of study medication, as defined in [section 7.2](#). Worst (maximum) post-baseline CTCAE grade is derived with all measurements from the first dose administration of study medication to no more than 37 days after the last dose of study medication or new anti-cancer therapies, which comes earlier. Otherwise, the shift table will be presented by ‘normal’, ‘abnormal but not clinically significant’, ‘abnormal and clinically significant’.

All CTCAE Grade 1 or higher abnormalities in laboratory tests will be flagged in the listings.

The incidence of patients with the following abnormal liver function tests (Hy’s Law) at any time post baseline will also be summarized:

HMPL-523

- ALT or AST  $\geq 3$  x ULN and  $\leq 5$  x ULN
- ALT or AST  $\geq 5$  x ULN
- Total bilirubin  $\geq 2$  x ULN
- (ALT or AST  $\geq 3$  x ULN) and total bilirubin  $\geq 2$  x ULN
- (AST or ALT  $\geq 3$  x ULN) and total bilirubin  $\geq 2$  x ULN and ALP  $< 2$  x ULN

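### The SAP closes the TEAE window 30 days after the last dose, while the protocol's TEAE definition and the SAP's other on-treatment rules run to at least day 37

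*SAP*

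**What the plan says.** **The 30-day rules.** SAP 17.2 defines a TEAE as an event with onset on or after first dose and "no later than 30 days after the date of last study treatment administration", or before new anti-neoplastic therapy if that comes first. The only later events admitted are drug-related SAEs. For missing or partial onset dates, SAP 7.9 presumes an event treatment-emergent unless it clearly began before first dose or "more than 30 days after last dose of study medication or new antineoplastic therapy".

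**The 37-day rules.**
- Protocol 7.3.3.2 counts events with onset on or after the start of treatment or with a missing onset date, and earlier events that "worsened in severity after the study treatment until 37 days after the last dose of study treatment".
- SAP 7.3 sets the on-treatment period "from the day of first dose of treatment to 37 days after the last dose of treatment", or to new therapy if earlier. It takes the worst post-baseline CTCAE grade over that period and names adverse events as well as laboratory results.
- SAP 17.4 takes the worst laboratory grade up to "no more than 37 days after the last dose of study medication".
- SAP 14.1 counts concomitant medications started "no later than 37 days following last administration date on treatment".
- SAP 14.2 counts procedures "no later than 37 days following the last administration date on treatment of study medication".
- The visit-window table in SAP 7.6 runs the completion or early-termination visit from "Last dose date of last cycle +1 to last dose date of last cycle +37".

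**Collection.** Protocol 6.3.1 collects all AEs to the later of 30 days after last dose and study discontinuation or termination. Under protocol 5.7.1 the safety visit is at 30 ± 7 days, and patients who stop the drug without progression stay on study with quarterly tumour follow-up.

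**Precedence.** SAP section 2 says the SAP overrides the protocol's statistical considerations, and that substantial differences will be identified. The SAP text that can be read does not identify this one. The modification history is redacted, so a note there cannot be ruled out.

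**The concern.** TEAE incidence by CTCAE grade is a secondary safety outcome (protocol 4.8.2). The narrower SAP window removes collected events from the tables that report it: overall TEAEs, TEAEs by grade, serious TEAEs, events of special interest, and TEAEs leading to death.

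It also leaves the report unable to reconcile with itself. Take a patient with a Grade 3 laboratory value on day 34, reported as a non-serious AE and treated with a new drug. The value enters the laboratory shift table and the drug enters the concomitant-medication table, but the event is missing from the TEAE and grade tables. The same patient is summarised over two different post-treatment windows.

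SAP 17.2 also omits the protocol's clause on events that began before treatment and then worsened.

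**Working it through.** **Where 37 comes from.** The safety visit is at 30 ± 7 days, so its late edge is 30 + 7 = 37 days. That reproduces the figure in protocol 7.3.3.2 and in the SAP's 37-day rules. The gap to SAP 17.2 is 37 − 30 = 7 onset days, days 31 to 37.

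**Two readings of the protocol.** In protocol 7.3.3.2 the 37-day phrase follows the worsening clause.
- If it limits the whole definition, new onsets count to day 37.
- If it limits only the worsening clause, new onsets have no end date.

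Onsets on days 31 to 37 are TEAEs on either reading, so the SAP is narrower both ways.

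**Which events change.** Assuming no new anticancer therapy has started:

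| Onset after last dose | Event | SAP 17.2 | 37-day rule |
|---|---|---|---|
| Day 30 | any | TEAE | TEAE |
| Days 31–37 | non-serious, related or not | not TEAE | TEAE |
| Days 31–37 | unrelated SAE | not TEAE | TEAE |
| Days 31–37 | related SAE | TEAE (exception) | TEAE |
| Day 38 | non-serious, or unrelated SAE | not TEAE | not TEAE |
| Day 38 | related SAE | TEAE (exception) | TEAE (exception) |

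The SAP's default of treating unclassifiable events as treatment-emergent does not help when the onset date is known. If new therapy starts before the event, SAP 17.2 and SAP 7.3 both exclude it, apart from related SAEs.

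**Share of the window.** Share = 7 / (days on drug + 37). The documents give no exposure figures, so days on drug are assumed.

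| Days on drug (assumed) | Calculation | Share |
|---|---|---|
| 28 | 7/65 | 10.8% |
| 61 | 7/98 | 7.1% |
| 183 | 7/220 | 3.2% |
| 365 | 7/402 | 1.7% |

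**Effect of one more patient in a row.** Cohort sizes are from protocol Table 2. All enrolled patients are assumed dosed, and the patient is assumed not already counted in that row.

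- Hodgkin's lymphoma: 1/25 = 4.0 points
- PTCL: 1/9 = 11.1 points
- CLL post-BTK: 1/7 = 14.3 points
- Stage 2 overall: 1/48 = 2.1 points

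**The case against.** The best defence of 30 days is that it is the minimum AE collection period for every patient. A window ending there covers only time with complete ascertainment; after day 30, collection depends on staying on study. It can be added that the SAP may override the protocol, and that the other 37-day rules may only reflect slack in the visit window. Protocol 5.5.1 and 5.6.4 require concomitant medications only to 30 days, yet SAP 14.1 counts them to 37. SAP 17.2.3 takes the maximum grade among TEAEs, so the AE grade tables can be produced under a 30-day rule without contradiction.

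Part of this stands. Ascertainment on days 31 to 37 is less even and should be disclosed. The protocol's limit on new onsets is ambiguous. It also has no new-therapy cut-off, so a 37-day SAP rule that keeps one still does not match it exactly. The share of the window is a share of calendar time; it equals a share of events only with a constant event rate and full collection on days 31 to 37. The 1/n figures show how sensitive a row is, not how likely it is to move.

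It does not rescue the 30-day rule. Collection runs to the later of two dates, and patients who stop without progression remain on study, so events on days 31 to 37 can be in the database and would be excluded by definition. The readable SAP does not declare the departure, as its section 2 says it would. Declaring it would still leave SAP 7.3, which names AE severity, at odds with SAP 17.2.

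**Conclusion.** The inconsistency is real and, applied as written, excludes collected non-serious events and unrelated SAEs with onset on days 31 to 37 from the TEAE summaries. It should be corrected before database lock.

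The numerical effect is probably small and cannot be estimated from the documents. Only patients still on study after day 30, and not yet on new anticancer therapy, can contribute. Related SAEs are already counted, the affected events stay in the any-AE row and the listings, deaths have their own summary (SAP 17.3), and DLTs are untouched. Restoring the worsening clause should change little, because protocol 6.4.3 and 6.4.7 already have a worsening recorded as an event.

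**What to change.** - Change 30 to 37 days in three places: the TEAE rule in SAP 17.2, the related-SAE exception in the same section, and the partial-date rule in SAP 7.9. The edit to the exception changes no count; it keeps the wording consistent.
- Keep the new-therapy cut-off, so that AEs, laboratory grades and concomitant medications share the window in SAP 7.3. Name that cut-off as a difference from protocol 7.3.3.2.
- Restore the protocol's clause on earlier events that worsen after treatment starts.
- Footnote the TEAE tables: onsets on days 31 to 37 are collected only from patients still on study.

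The cost is a few wording edits, one constant in the AE flag and one footnote. TEAE rates may rise slightly, and ascertainment in the last seven days is less even. If the sponsor prefers 30 days, the SAP must state and justify it as a departure from the protocol and must also reconcile SAP 7.3 with it.
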